5.8.6 Surgeries

Surgeries and procedures collected on the eCRF page for Surgery and Procedure History Assessment are summarized separately for previous surgeries and procedures and during study conduct. All events will be listed (UXPL_01). A listing of surgeries and procedures will be generated

UXPT_01: Surgeries and Procedures

	Arm
A	
Surgery/Procedure (N=xx)	
<hr/>	
Total number of patients with at least one surgery/procedure x.x%)	xx (
Total number of surgeries/procedures	xx
ARTHROSCOPIC SYNOVECTOMY KNEE JOINT x.x%)	x (
CRANIOTOMY (xx.x%)	xx

For frequency counts by surgery/procedure, multiple occurrences of the same surgery in an individual are counted only once. For frequency counts of "Total number of surgeries/procedures" rows, multiple occurrences of the same surgery in an individual are counted separately.

UXPL_01: Listing of Surgeries and Procedures history

Protocol: xxnnnnn

Center/Patient ID Age/Sex/Race	Surgery/Procedure	Study Day of Onset	Relative Start of Procedure/Surgery	Study Period (1)
	Phebotomy	NA	BEFORE SCREENING	1
	Splenectomy	135		2

5.8.7 Previous and Concomitant Medications

Non-study medication collected on the eCRF page will be categorized as either previous, previous-concomitant or concomitant. The derivation is performed by STREAM within the analysis dataset. The algorithm for each category is defined below.

A medication is considered concomitant if the start date/time is on or after the date/time of Study Day 1. These medications will be labelled 'CONCOMITANT' in the analysis dataset.

Otherwise a medication is considered previous if the end date/time is not missing and is before the datetime of Study Day 1. These medications will be labelled 'PRIOR' in the analysis dataset.

Otherwise a medication is considered previous-concomitant, and will be labelled 'PRIOR_CONCOMITANT' in the analysis dataset.

Summary tables will be based on the CMT01 template and will include:

- Previous Medications
- Previous/Concomitant Medications, excluding PV Medications
- Concomitant Medications, excluding PV Medications

The medications will also be listed (UCML_01).

CML01: Listing of Previous and Concomitant Medications

Treatment: CONTROL; N=XX

Center/Patient ID	Medication Class	Medication Name	Age/Sex/Race	Date of First Administration	Study Drug	Medication Start Date	Study Day	Duration (days)	Previous?	Ongoing at final contact?	Dose	
CORTICOSTEROIDS												
	DEXAMETHASONE							-1	5	Yes	No	4
mg	xxx	Y						5	7	No	No	2
	DEXAMETHASONE							11	1	No	No	10
mg	XXXX	Y						11	4	No	No	5
	DEXAMETHASONE							14		No	Yes	5
mg	XXXX	N										
	DEXAMETHASONE											
mg	XXXX	Y										
CORTICOSTEROIDS												
	PREDNISOLONE SODIUM							-14	17	Yes	No	20
mg	XXXX	N						4	10	No	No	20
	METASULFOBENZOATE							14	25	No	No	40
mg	XXXX	N						39	6	No	No	30
	PREDNISOLONE SODIUM							67	7	No	No	20
mg	XXXX	N										
	METASULFOBENZOATE											
mg	XXXX	N										
	PREDNISOLONE SODIUM											
mg	XXXX	N										
	METASULFOBENZOATE											
mg	XXXX	N										

CMT01 Concomitant Medications

Class	(N=xx)
Other Treatment	
<hr/>	
Total number of patients with at least one treatment (xx.x%)	xx
Overall total number of treatments	xx
ANALGESIC/OTHER DRUG COMBINATIONS	
Total number of patients with at least one treatment (xx.x%)	xx
Total number of treatments	x
HYDROCODONE TARTRATE/PARACETAMOL	
(xx.x%)	xx
ANALGESICS	
Total number of patients with at least one treatment x.x%)	x (
Total number of treatments	x
PARACETAMOL	
x.x%)	x (
OXYCODONE HYDROCHLORIDE/PARACETAMOL	
(xx.x%)	xx

Multiple uses of a specific medication for a patient were counted once in the frequency for the medication. Likewise, multiple uses within a specific medication class for a patient were counted once in the frequency for the medication class.

L_CM_GLOSS: Glossary of Medication Coded Terms

Medication Class Reported Name of Drug, Med, or Therapy	Standardized Medication Name
--	------------------------------

5-HT1 AGONISTS ZOMIGORO	ZOLMITRIPTAN
----------------------------	--------------

5-HT3 ANTAGONISTS ONDANSETRON	ONDANSETRON
----------------------------------	-------------

ADRENERGICS/SYPATHOMIMETICS EPIPE	EPINEPHRINE
--------------------------------------	-------------

5.8.8 Targeted - Polycythemia medications

Anti-emetic prophylaxis is mandatory in Cycle 1.

Table 23 Targeted - Polycythemia medications

	ARM A (N=xxx)
Overall	
No. of patients who received at least one	xx (xx.x%)
GCSF	
5HT3-RA	xx (xx.x%)
DEXAMETHASONE	xx (xx.x%)
LORAZEPAM	xx (xx.x%)
NK1-RA	
etc...	
 Cycle 1*	
No. of patients who received at least one	xx (xx.x%)
GCSF	
5HT3-RA	xx (xx.x%)
DEXAMETHASONE	xx (xx.x%)
LORAZEPAM	xx (xx.x%)
NK1-RA	
 Cycle 2**	
No. of patients who received at least one	xx (xx.x%)
GCSF	
5HT3-RA	xx (xx.x%)
DEXAMETHASONE	xx (xx.x%)
LORAZEPAM	xx (xx.x%)
NK1-RA	
 Cycle 3**	
No. of patients who received at least one	xx (xx.x%)
GCSF	
5HT3-RA	xx (xx.x%)
DEXAMETHASONE	xx (xx.x%)
LORAZEPAM	xx (xx.x%)
NK1-RA	
Etc...	

*Any dose of GCSF that occurred within 14 days before the start of cycle 1 and was administered before the start of cycle 2 (the day before the start of cycle 2).

**Any dose of GCSF that occurred from the start of the cycle to the day before the next cycle..

Note: This table is produced using data from the eCRF page Targeted Concomitant Medications (G-CSF).

All treatments corresponding to CMCAT = GCSF will be listed by cycle and overall

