6.1.1 Pre-medication and Prophylaxis

Nausea and vomiting have been commonly observed in idasanutlin studies. In some cases, they have led to treatment discontinuation.

- *Treatment to mitigate emesis must be given prophylactically prior to each cycle as follows: At least 30–60 minutes (timing depending on use of transdermal or oral 5-HT₃-receptor antagonist [RA]) before start of a treatment cycle and on each treatment day for dexamethasone administer:*
 - *Long-acting 5-HT₃-RA orally or intravenously (IV) on Day 1 (preferably palonosetron IV 0.25 mg or oral 0.5 mg) 30–60 minutes prior to idasanutlin administration or granisetron transdermal system ≥24 hours to a maximum of 48 hours prior to idasanutlin administration*

If the above recommended 5-HT₃-RAs are not available, treatment with short-acting 5-HT₃-RAs (e.g., 8 mg ondansetron) is mandatory 30 minutes prior to intake of idasanutlin on all treatment days (an extra dose of 8 mg ondansetron can be taken if symptoms appear later on treatment days, with a minimum of 8 hours between ondansetron doses).

AND

- *Dexamethasone 12 mg orally/IV on Day 1 (30–60 minutes before idasanutlin), then 8 mg orally on Days 2–5*

Investigators are to choose IV/oral/transdermal system administration at their discretion.

- *Anticipatory nausea: If the patient experiences nausea during the first cycle, consider adding anxiolytics, like lorazepam, from Cycle 2 onwards.*
- *Additional prophylaxis on top of the long-acting 5-HT₃-RA and dexamethasone is allowed per site local guideline and experience.*

Decrease in intensity of prophylaxis following Cycle 1 may be utilized based on investigator discretion, in agreement with the Medical Monitor, and patient tolerability.

All premedications for prophylaxis and on-study modifications should be captured on the patient's concomitant medications eCRF, indicating as intended for prophylaxis. The adverse GI events in the Phase I idasanutlin studies primarily included nausea, *diarrhea*, vomiting, abdominal pain, constipation, and anorexia. Supportive therapies for diarrhea and nausea are encouraged in this study.

See Section 8.3.9 for guidance for management of AEs and prophylaxis in subsequent cycles.

Re-dosing of study medication after emesis:

If vomiting occurs within 15 minutes of administering study medication and whole tablets are still intact, another dose may be administered, and the second dose must be

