6.5 CONCOMITANT THERAPY

6.5.1 Permitted Therapy

Any medication or vaccine (including over-the-counter or prescription medicines, approved dietary and herbal supplements, nutritional supplements) used by a patient from 28 days prior to screening until the final visit or EOS must be recorded along with reason for use, dates of administration (including start and end dates, or if ongoing).

The Medical Monitor should be contacted if there are any questions regarding concomitant or prior therapy.

All concomitant medications should be recorded on the Previous and Concomitant Treatments eCRF.

All concomitant medications to treat PV related symptoms as defined in Section 8.3.8 should be recorded on the Previous and Concomitant Treatments (Targeted - Polycythemia Vera Associated) eCRF.

All therapy and/or medication administered to manage AE should be recorded on the AE eCRF.

Patients who use oral contraceptives, hormone-replacement therapy, or other maintenance therapy should continue their use.

The use of inhaled corticosteroids and mineralocorticoids (e.g., fludrocortisone) for patients with orthostatic hypotension or adrenocortical insufficiency is allowed.

Megestrol administered as an appetite stimulant is acceptable when the patient is enrolled in the study.

Since nausea is a commonly reported AE in previous studies, *anti-emetic prophylaxis is mandatory prior to each cycle, unless otherwise agreed upon between the investigator and the Medical Monitor.* The use of anti-emetic agents should be documented in the eCRF (see Section 6.1.1).

Phlebotomy can occur anytime it is clinically warranted per institutional guidelines. Any phlebotomies prior to Study C1D1 (up to 1 year) and while on study will be individually entered on the Previous and Concomitant Treatments (Phlebotomy) eCRF.

Institutional guidelines for use of growth factor support, transfusions, and antibiotics should be followed with consideration for prohibited medications (Section 6.5.2).

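### SAP 5.8.8 fills the polycythemia-medication table from a G-CSF page, so on-study PV-symptom drugs, already excluded from the SAP 5.8.7 tables, reach no summary table

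*SAP*

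**What the plan says.** **Commitment.** Concomitant medication is among the secondary safety endpoints (Protocol Table 3). Protocol Table 11 says it will be shown in both summary tables and listings.

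**Where the protocol records the drugs.**
- Symptom treatment, Protocol 6.5.1: "All concomitant medications to treat PV related symptoms as defined in Section 8.3.8 should be recorded on the Previous and Concomitant Treatments", on the page labelled Targeted - Polycythemia Vera Associated. Section 8.3.8 names the same page.
- Antiemetic prophylaxis, Protocol 6.1.1: premedications "should be captured on the patient's concomitant medications eCRF, indicating as intended for prophylaxis".

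**What SAP 5.8.7 tabulates.** Three summaries use the CMT01 template. Previous Medications has no exclusion. The other two are "Previous/Concomitant Medications, excluding PV Medications" and "Concomitant Medications, excluding PV Medications". A listing (UCML_01) has no stated exclusion. The SAP does not say what counts as a PV medication.

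**What SAP 5.8.8 tabulates.** Table 23 is titled for targeted polycythemia medications. Its named rows are GCSF, 5HT3-RA, dexamethasone, lorazepam and NK1-RA, and the overall block ends with an open 'etc.'. Its timing footnotes deal with G-CSF doses only. Its source note is "This table is produced using data from the eCRF page Targeted Concomitant Medications (G-CSF", and below it stands "All treatments corresponding to CMCAT = GCSF will be listed by cycle and overall".

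**Prophylaxis.** SAP 5.8.8: "Anti-emetic prophylaxis is mandatory in Cycle 1". Protocol 6.1.1: "Treatment to mitigate emesis must be given prophylactically prior to each cycle as follows".

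**The concern.** A drug class taken out of the general tables should come back in a table of its own. Here the table with the matching title has no PV-therapy row, a source page unknown to the protocol and a listing filter that admits G-CSF alone. A programmer following these instructions would deliver a table that does not contain what its title says.

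The drugs that drop out matter for interpretation. They treat the symptoms listed in Protocol 8.3.8, and Protocol Appendix 1 uses that same list for the symptom criterion of ELN complete response. They also bear on the MPN-SAF TSS results. With a single arm, there is no control group in which the same symptom treatment would show, so the reader depends on a summary of who took what.

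The by-cycle antiemetic rows matter for a related reason. Protocol 6.1.1 allows prophylaxis to be reduced in intensity after Cycle 1, so use can differ between cycles. Table 23 is the only by-cycle view of it that the SAP specifies.

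**Working it through.** The documents give no figure to reproduce and no arithmetic is needed beyond counting tables. The check follows each kind of medication from the page where the protocol records it to the SAP output meant to show it.

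**Step 1: which CMT01 tables can hold on-study use.** SAP 5.8.7 sorts records by date. A drug started on or after Study Day 1 is concomitant. A drug with an end date before Study Day 1 is previous. Everything else is previous-concomitant. On-study use can therefore fall only in the second and third groups. Both of the corresponding tables exclude PV Medications, so of three CMT01 tables, two cover on-study use and none of those two shows PV medications.

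**Step 2: whether SAP 5.8.8 puts them back.** Of the five named rows, one is G-CSF and four are antiemetic or anxiolytic. None is a PV therapy. The source note and the category filter both point to G-CSF records.

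**Step 3: trace by medication type.**

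| Medication | Recorded on | SAP output | Result |
|---|---|---|---|
| On-study PV-symptom drugs | Targeted - Polycythemia Vera Associated eCRF (Protocol 6.5.1, 8.3.8) | Excluded from both on-study CMT01 tables; SAP 5.8.8 reads another page | No summary table; UCML_01 listing at most |
| Antiemetic prophylaxis | Concomitant medications eCRF, flagged (Protocol 6.1.1) | CMT01 concomitant table by class and drug; SAP 5.8.8 by cycle | Overall summary present; by-cycle rows point to the wrong page |
| PV therapy before Day 1 | PV history and prior-therapy page (SAP 5.6) | UMHT02; Previous Medications, no exclusion | Summary planned, although the UMHT02 shell shows conditions |
| Prior phlebotomy | Phlebotomy eCRF (Protocol 6.5.1) | SAP 5.8.5 | Summary planned |

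Only the first row fails completely. The second fails in part.

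**Step 4: the undefined term.** If PV Medications means the records on the PV-associated page, which fits the title of SAP 5.8.8, the table above stands. If it means the drugs shown in Table 23, antiemetics leave CMT01 as well. If it means only therapy directed at PV itself, symptom drugs might stay in CMT01, depending on which pages those tables read, and SAP 5.8.7 does not specify that. The SAP gives no basis for choosing, so different programmers could produce different tables.

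**The case against.** The strongest reply is that this is leftover template text and not a decision to omit anything. Neighbouring SAP shells still carry bendamustine, obinutuzumab and infusion-rate rows, and the plots in SAP 5.9 show another study's number and treatment arms. The SAP 5.8.8 title matches the protocol's page name, and its rows are left open. The full set of outputs is in a separate List of Planned Outputs that is not among the documents, and it could include a PV-medication table built on an existing template.

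The origin is probably as described, but it does not remove the problem. The source note and the category filter are programming instructions, and SAP Section 5 says its specifications should be detailed enough to program from. The missing output list is a fair limit on how firmly the conclusion can be put.

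Three further objections stand, each against a stronger reading that a reader might draw.

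- A reader might infer that antiemetic use is summarised nowhere. Under Protocol 6.1.1 these drugs are recorded on the general concomitant page, and on the ordinary meaning of the term they are not PV medications. The SAP's own medication shells show dexamethasone and ondansetron among general drugs. Only the by-cycle view is at risk.
- A reader might infer that prohibited hydroxyurea or other cytoreduction could go unseen and inflate the response rate. The page at issue is assigned to drugs for the Section 8.3.8 symptoms, not to cytoreduction. Such therapy is prohibited by Protocol 6.5.2, and SAP 5.3 and 5.4 list and summarise major deviations. How such a patient would count for response before Week 32 is a separate question.
- A reader might put a cost on this in percentage points of response. Changing the source page of a medication table changes no patient's response.

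**Conclusion.** The plan is wrong as written on a narrow point. On-study PV-symptom medication reaches none of the summary tables specified in the SAP, contrary to Protocol Table 11, and appears at most in the general listing. The by-cycle antiemetic rows also name a source where the protocol does not record those drugs, while the overall antiemetic summary should survive in CMT01.

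The size is one medication type without a summary and one by-cycle display with a wrong source, both within a secondary safety endpoint. No efficacy estimate is affected.

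The conclusion assumes that PV Medications refers to what the PV-associated eCRF collects, that the eCRF pages are as the protocol describes them, and that the separate output list does not already correct the source.

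The SAP and protocol statements on prophylaxis also disagree. The SAP speaks of Cycle 1. The protocol speaks of every cycle, with an exception by agreement with the Medical Monitor (6.5.1) and a possible reduction in intensity after Cycle 1 (6.1.1). These passages must be reconciled, and this review takes no position on which rule is right.

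**What to change.** In the SAP:

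1. Define PV Medications in 5.8.7, preferably by eCRF page, and state which pages feed each CMT01 table.
2. In 5.8.8, source the PV table and its listing from the Targeted - Polycythemia Vera Associated eCRF, shown by class and cycle.
3. Take the by-cycle antiemetic rows from concomitant medications eCRF records flagged as prophylaxis, with patients starting that cycle as the denominator.
4. Remove the G-CSF category restriction for these outputs. If a G-CSF table is wanted, specify it separately with its true source page.
5. Reconcile the SAP's prophylaxis sentence with Protocol 6.1.1 and 6.5.1, including the exceptions stated there.
6. Check the List of Planned Outputs against these changes.

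The cost is SAP wording and table programming on data the protocol already collects. No response definition changes.

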5.9 Clinical Outcome Assessment Analysis

The MPN-SAF TSS, EORTC QLQ-C30, and PGIC will be used to measure symptoms of PV, global health status/quality of life (GHS/QoL), functioning, and change in condition. Data will be used to derive summary scores at each timepoint. Appropriate summary statistics (frequency, mean, standard deviation, median, and range) of absolute scores will be calculated for the PGIC, all scales of the MPN-SAF TSS, and the GHS/QoL & functioning scales of the EORTC QLQ-C30, at each assessment point, for all patients. Line graphs will be used to chart mean-level change over the course of the study. Mean change from baseline to each follow-up assessment point will be calculated for the scales of the MPN-SAF TSS and EORTC QLQ-C30. Frequencies will be used to show the distribution of responses to the PGIC at each assessment point. Results will be further stratified by splenomegaly at baseline. COA completion and compliance rates will be summarized at each assessment point with reasons for missing data.

5.9.1 MPN-Symptom Assessment Form Total Symptom Score (MPN-SAF TSS)

Separate tables of MPN-SAF TSS scores & change from baseline will be provided at each visit across all scales (early satiety, abdominal discomfort, and weight loss to be stratified by splenomegaly at baseline)

Line Plots of median change from baseline symptom scores will be provided over time

PROT02: MPN-SAF TSS scores with splenomegaly and Change from Baseline by
 Visit: Intent-to-Treat Patients

Protocol: xxnnnnn

Item: Filling up quickly when you eat (Early Satiety) / Abdominal discomfort/
 Unintentional Weight Loss 6 Months (Weight loss)

Patients (N=xx)	Ruxolitinib Naïve (N=xx)		Ruxolitinib Exposed (N=xx)		All	
	Value at Visi t	Change from Baselin e	Value at Vis it	Change from Baselin e	Value at Visi t	Change from Baseline
CYCLE 2 DAY 1						
n	nn		nn		nn	
Mean (SD)	xx.x (xx.x)		xx.x (xx.x)		xx.x (xx.x)	
95% CI	xx.x - xx.x		xx.x - xx.x		xx. x - xx. x	
Median	xx.x		xx.x		xx. x	
Q1-Q3	xx.x-xx.x		xx.x-xx.x		xx.x-xx.x	
Min-max	xx.x-xx.x		xx.x-xx.x		xx.x-xx.x	
CYCLE 5 DAY 1						
n	nn n	nn n	nnn	nn n	nn n	nn n
Mean (SD)	xx.x (xx.x)	xx.x (xx.x)	xx.x (xx.x)	xx.x (xx.x)	xx.x (xx.x)	xx.x (xx.x)
95% CI	xx.x - xx.x	xx.x - xx.x	xx.x - xx.x	xx. x - xx. x	xx. x - xx. x	xx.x - xx.x
Median	xx.x	xx.x	xx.x	xx. x	xx. x	xx.x
Q1-Q3	xx.x -xx.x	xx.x-xx.x	xx.x-xx.x	xx.x-xx.x	xx.x-xx.x	xx.x-xx.x
Min-max	xx.x -xx.x	xx.x-xx.x	xx.x-xx.x	xx.x-xx.x	xx.x-xx.x	xx.x-xx.x
CYCLE X DAY Y						
n	nn n	nn n	nnn	nn n	nn n	nn n
Mean (SD)	xx.x (xx.x)	xx.x (xx.x)	xx.x (xx.x)	xx.x (xx.x)	xx.x (xx.x)	xx.x (xx.x)
95% CI	xx.x - xx.x	xx.x - xx.x	xx.x - xx.x	xx. x - xx. x	xx. x - xx. x	xx.x - xx.x
Median	xx.x	xx.x	xx.x	xx. x	xx. x	xx.x
Q1-Q3	xx.x -xx.x	xx.x-xx.x	xx.x-xx.x	xx.x-xx.x	xx.x-xx.x	xx.x-xx.x
Min-max	xx.x -xx.x	xx.x-xx.x	xx.x-xx.x	xx.x-xx.x	xx.x-xx.x	xx.x-xx.x

Note: Visit will be populated as per the protocol time point assessments.

PROT02:MPN-SAF TSS scores without splenomegaly and Change from Baseline by Visit: Intent-to-Treat Patients

Protocol: xxnnnnn

[figure not shown]
Item: Fatigue/ Inactivity/ Problems with Concentration Compared to Prior to my MPD/ Night Sweats/ Itching/ Bone Pain/ Fever

All Patients (N=xx)	Ruxolitinib Naïve (N=xx)		Ruxolitinib Exposed (N=xx)		Value at Visit	Change from Baseline
	Value at Visit	Change from Baseline	Value at Visit	Change from Baseline		
CYCLE 2 DAY 1						
n	nnn		nnn		nnn	
Mean (SD)	xx.x (xx.x)		xx.x (xx.x)		xx.x (xx.x)	
95% CI	xx.x - xx.x		xx.x - xx.x		xx.x -	
Median	xx.x		xx.x		xx.x	
Q1-Q3	xx.x-xx.x		xx.x-xx.x		xx.x-xx.x	
Min-max	xx.x-xx.x		xx.x-xx.x		xx.x-xx.x	
CYCLE 5 DAY 1						
n	nnn	nnn	nnn	nnn	nnn	
Mean (SD)	xx.x (xx.x)	xx.x (xx.x)	xx.x (xx.x)	xx.x (xx.x)	xx.x (xx.x)	
95% CI	xx.x - xx.x	xx.x - xx.x	xx.x - xx.x	xx.x -	xx.x -	
Median	xx.x	xx.x	xx.x	xx.x	xx.x	
Q1-Q3	xx.x -xx.x	xx.x-xx.x	xx.x-xx.x	xx.x-xx.x	xx.x-xx.x	
Min-max	xx.x -xx.x	xx.x-xx.x	xx.x-xx.x	xx.x-xx.x	xx.x-xx.x	
CYCLE X DAY Y						
n	nnn	nnn	nnn	nnn	nnn	
Mean (SD)	xx.x (xx.x)	xx.x (xx.x)	xx.x (xx.x)	xx.x (xx.x)	xx.x (xx.x)	
95% CI	xx.x - xx.x	xx.x - xx.x	xx.x - xx.x	xx.x -	xx.x -	
Median	xx.x	xx.x	xx.x	xx.x	xx.x	
Q1-Q3	xx.x -xx.x	xx.x-xx.x	xx.x-xx.x	xx.x-xx.x	xx.x-xx.x	
Min-max	xx.x -xx.x	xx.x-xx.x	xx.x-xx.x	xx.x-xx.x	xx.x-xx.x	

Note: Visit will be populated as per the protocol time point assessments.

PROG02: Plot of Median Symptom score Change from Baseline by Visit: Intent-to-Treat Patients
 Protocol: xxnmmn

Plot of Change from Baseline in BFI Interference Scale by Time Point
 Protocol: WO29074

	Planned Arm Code																												
	●	●	●	●	●	●	●	●	●	●	●	●	●	●	●	●	●	●	●	●									
	Combination	MPDL3280A	Sunitinib																										
Sunitinib	93	89	79	76	69	63	62	59	53	41	37	32	25	21	20	19	17	13	10	9	7	5	5	4	4	4	3	2	1
MPDL3280A	94	86	81	82	64	62	61	61	48	45	37	34	23	23	21	15	11	10	11	7	6	4	4	3	2	2	1	1	1
Combination	95	90	85	80	75	74	72	66	57	56	50	40	36	32	28	26	24	23	18	13	10	9	8	5	4	2	1	1	

5.9.2 Patient Global Impression of Change

A table showing frequencies of response distributions for each assessment time point will be provided.

PGIT01

PGIC Distribution of by Visit
Intent-to-treat Patients
Protocol: {base protocol}

Cycle 2 day 1	Ruxolitinib Naïve (N=xx)	Ruxolitinib Exposed (N=xx)	All Patients (N=xx)
Very Much Improved	xx (xx.x%)	xx (xx.x%)	xx (xx.x%)
Much Improved	xx (xx.x%)	(x.xx, x.xx)	(x.xx, x.xx)
Minimally Improved	xx (xx.x%)	xx (xx.x%)	xx (xx.x%)
No Change	xx (xx.x%)	xx (xx.x%)	xx (xx.x%)
Minimally Worse	xx (xx.x%)	xx (xx.x%)	xx (xx.x%)
Much Worse	xx (xx.x%)	xx (xx.x%)	xx (xx.x%)
Very Much Worse	xx (xx.x%)	xx (xx.x%)	xx (xx.x%)
Not Assessed	xx (xx.x%)	xx (xx.x%)	xx (xx.x%)
Cycle 5 day 28	nn(xx.x%)	nn(xx.x%)	nn(xx.x%)
Very Much Improved	xx (xx.x%)	xx (xx.x%)	xx (xx.x%)
Much Improved	xx (xx.x%)	(x.xx, x.xx)	(x.xx, x.xx)
Minimally Improved	xx (xx.x%)	xx (xx.x%)	xx (xx.x%)
No Change	xx (xx.x%)	xx (xx.x%)	xx (xx.x%)
Minimally Worse	xx (xx.x%)	xx (xx.x%)	xx (xx.x%)
Much Worse	xx (xx.x%)	xx (xx.x%)	xx (xx.x%)
Very Much Worse	xx (xx.x%)	xx (xx.x%)	xx (xx.x%)
Not Assessed	xx (xx.x%)	xx (xx.x%)	xx (xx.x%)

Note: We will present as per protocol assessments.

5.9.3 European Organization for the Research and Treatment of Cancer Quality of Life Questionnaire-Core 30 (EORTC QLQ-C30)

General principles of scoring:

The QLQ-C30 is composed of both multi-item scales and single-item measures. These include five functional scales, three symptom scales, a GHS / QoL scale, and six single items. Each of the multi-item scales includes a different set of items - no item occurs in more than one scale. All of the scales and single-item measures range in score from 0 to 100. A high scale score represents a higher response level.

Thus a high score for a functional scale represents a high / healthy level of functioning, a high score for the GHS / QoL represents a high QoL, but a high score for a symptom scale / item represents a high level of symptomatology / problems.

The principle for scoring these scales is the same in all cases:

1. Estimate the average of the items that contribute to the scale; this is the raw score.
2. Use a linear transformation to standardise the raw score, so that scores range from 0 to 100; a higher score represents a higher ("better") level of functioning, or a higher ("worse") level of symptoms.

The Linear transformed scores are derived as follows:

For functional scale:

